#### 7.7.2.2. Average CSMS over the entire GPS

The average CSMS over the entire GPS is calculated in the same way as the average CSMS over the peak GPS. The following null and alternative hypotheses will be tested for this endpoint, based on all subjects who received at least 1 injection of the clinical trial medication, i.e., are included in the FAS (two-sided test):

H0:  $\mu$ Placebo =  $\mu$ PQ Grass

*H*1:  $\mu$ *Placebo*  $\neq \mu$ *PQ Grass* 

 $\mu$ : arithmetic mean of the average CSMS over the entire GPS.

The primary efficacy analysis will be repeated for the average CSMS over the entire GPS. Summary statistics will be provided for the average CSMS over the entire GPS by treatment group.

## 7.7.2.3. Average dSS and dMS over the peak and the entire GPS

The average dSS over the peak and the entire GPS and the average dMS over the peak and the entire GPS is calculated in the same way as the average CSMS over the peak GPS.

The following null and alternative hypotheses will be tested for these endpoints, based on all subjects who received at least 1 injection of the clinical trial medication, i.e., are included in the FAS (two-sided test):

H0:  $\mu$ Placebo =  $\mu$ PQ Grass

H1:  $\mu$ Placebo  $\neq \mu$ PQ Grass

 $\mu$ : arithmetic mean of the average dSS/dMS over the peak / entire GPS.

Summary statistics will be provided for all average scores by treatment group.

7.7.2.4.2. Key secondary efficacy analysis of well days during peak GPS using generalised estimating equation The probability of a well day during the peak GPS will be analysed using data on a by-day level per subject using generalised estimating equation (GEE).

The following null and alternative hypotheses will be tested for this endpoint, based on all subjects who received at least 1 injection of the clinical trial medication, i.e., are included in the FAS (two-sided test):

H0: pPlacebo = pPQ Grass

#

H1: pPlacebo pPQ Grass

p: probability of well days during the peak GPS

Thereby, the expected probability for a well day on a specific day of the peak GPS will be modelled in terms of a GEE for a binary response. As the observations of well days for one subject during the peak GPS are correlated (it can be assumed that days close to each other have a higher correlation than more distant days), a within-subject working correlation matrix is assumed.

#### 7.7.2.5. Serum grass-specific IgG4 at Visit 7 compared to baseline

Blood samples are collected at screening, Visit 7 and Visit 10 for the evaluation of several immunoglobulin parameters, including grass-specific IgG4 [mg/L].

Summary statistics will be created by visit and treatment group for the absolute values (Baseline, Visit 7 and Visit 10) and the absolute change from baseline (to Visit 7 and Visit 10).

The change from baseline to Visit 7 in grass-specific IgG4 [mg/L] will be additionally analysed using the same linear mixed model as specified in the primary analysis with the baseline value as additional covariate.

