#### **Overall Design (Brief Summary):**

This is a multi-centre, randomised, parallel group, double-blind, placebo-controlled clinical trial to confirm the efficacy and safety of the optimal effective dose of PQ Grass (27600 SU). The trial will have an adaptive group sequential design with one planned interim analysis.

Subjects will be assigned in a ratio of 1:1 (PQ Grass:Placebo) with treatment course to be completed prior to the onset of the grass pollen season (GPS):

- **PQ Grass:** 6 injections of PQ Grass (900, 2700, 6000, 6000, 6000, 6000 SU sequentially) *or*
- **Placebo:** 6 injections of placebo

The study includes 4 periods, encompassing 11 visits to the study site and at least 2 follow-up telephone calls. Subjects will be provided with enough relief medication to cover them through this period by the study site.

**Period 1** (Screening [Visit  $1 \pm \text{Visit 1a}$ ]): This includes the screening visit at which subjects' eligibility for the clinical trial will be assessed.

**Period 2** (Randomisation and treatment [Visit 2 to Visit 7]): At Visit 2, subjects will be randomly allocated in a randomisation ratio of 1:1 to the active treatment (PQ Grass) or the placebo treatment group and will receive the first injection.

After Randomization at Visit 2, subjects will thereafter return to the study site at subsequent visits during the treatment period (Visit 3 to Visit 7) to receive the remaining injections. The average duration of the treatment period will be approximately 16 weeks.

Treatment with either 6 injections of active treatment (900, 2700, 6000, 6000, 6000 and 6000 SU sequentially) to achieve a cumulative nominal dose of 27600 SU, or 6 injections of placebo will be administered prior to the onset of the GPS.

**Period 3** During the GPS, subjects will record their allergic rhinitis/rhinoconjunctivitis symptoms and use of relief medications in an electronic diary (eDiary). The symptom and medication scores during the peak GPS and the entire (or truncated) GPS calculated according to the European Academy of Allergy and Clinical Immunology (EAACI) recommendations for the CSMS (primary endpoint) will be compared between the active and placebo treatment groups. The following 4 visits will be performed:

- Visit 8 (pre-GPS)
- Visit 9 ( $\approx$  onset of GPS)
- Visit 10 (during GPS)
- Visit 11 ( $\approx$  end of GPS)

Protocol: PQGrass306

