#### Dose/Dose schedule:

PQ Grass or placebo will be administered during Visits 2 to 7. Visits 2 to 4 will be approximately 1 week apart, Visit 5 to 7 will be approximately 4 weeks apart.

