**Table 1 Objectives and endpoints** 

Table 1 Objectives and endpoints Objectives	Endpoints
Primary Efficacy	
To evaluate the efficacy of PQ Grass 27600 SU in subjects with grass pollen induced seasonal allergic rhinitis (SAR) and/or rhinoconjunctivitis based on symptoms and medications.	Combined Symptom and Medication Score (CSMS) averaged over the peak grass pollen season (GPS).
Secondary Efficacy	
To evaluate the potential of PQ Grass 27600 SU to reduce symptom burden and the need for medication use.	The number of well days during the peak GPS.
To evaluate the quality of life.	Rhinoconjunctivitis quality of life questionnaire with standardised activities (RQLQ(S)) measured within the peak GPS.
To evaluate the effect of PQ Grass 27600 SU on IgG4.	Serum grass-specific IgG4 at Visit 7 compared to baseline.
To evaluate the treatment effect of PQ Grass on the CSMS over the entire GPS.	CSMS averaged over the entire (or truncated) GPS.
To evaluate the treatment effect of PQ Grass on the daily Symptom Score (dSS) and daily	dSS component of the CSMS averaged over the peak GPS and entire (or truncated) GPS.
Medication Score (dMS) components of the CSMS over the GPS.	dMS component of the CSMS averaged over the peak GPS and entire (or truncated) GPS.
Safety	
To evaluate the safety and tolerability of PQ Grass in subjects with grass pollen induced SAR	Frequency, severity and relationship of adverse events (AEs) to treatment.
and/or rhinoconjunctivitis.	Frequency of AEs leading to premature discontinuation from treatment or clinical trial.
	Frequency of adverse events of special interest (AESIs).
	Changes in clinical laboratory values (serum chemistry, haematology and urinalysis) between screening and Visit 11.
	Changes in vital signs at all treatment visits.

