## 7.7.2 Key secondary efficacy analyses

The key secondary efficacy endpoints will only be addressed with statistical hypothesis tests if the primary endpoint shows a statistically significant difference between treatment groups. Multiplicity in the key secondary endpoints will be addressed with the Fallback method. The full 5.0% two-sided alpha for the Fallback method will be distributed across the 8 key secondary endpoints. If the preceding hypothesis test is not significant, subsequent tests will be performed at the aforementioned alpha-level. If tests are significant, the alpha is added to the subsequent hypothesis test.

All p-values for the analyses of key secondary endpoints will be presented without adjusting for multiplicity. The evaluation whether the null hypotheses can be rejected or not will be done based on the raw p-values. Cls (for example for the LS means) will also be presented in an explorative way, i.e., two-sided 95% Cls will be presented without a formal multiplicity adjustment.

This document is based on

BM-04-DFC01

Document Standard for Statistical Analysis Plan (SAP) v 14.0

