## 7.8.1 Investigational drug/placebo exposure and compliance

The number and percentage of subjects having received treatment will be summarised per treatment group and treatment visit (scheduled injections as well as unscheduled injections for dose repeat and dose reduction ) for the FAS (randomised treatment) and the SAF (actual treatment).

The actually received cumulative dose in SU is calculated based on the actually received kit and vial numbers entered in the eCRF. The planned cumulative dose is based on the randomised treatment (27600 SU for the PQ Grass treatment group).

Summary statistics will be provided for the number of injections received, the actually received cumulative dose in SU and the ratio of the cumulative dose actually received and planned [%]. This ratio can only be calculated for the PQ Grass treatment group and the corresponding planned cumulative dose is 27600 SU for every subject. Please note that ratios greater than 100% might result for subjects receiving additional unscheduled injections. This summary will be provided for the FAS (randomised treatment) and the SAF (actual treatment).

Any subject with dose modifications or unscheduled injections will be listed in a separate listing providing all details on all injections received.

For this clinical trial, any dose of investigational drug/placebo greater than the dose prescribed (for each of the dosing visits) within the clinical trial protocol represents an overdose. A separate listing will be generated including only subjects that experienced an overdose.

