#### 7.8.4 Vital signs

Vital signs (systolic and diastolic blood pressure, pulse rate, respiratory rate, and body temperature) will be measured in a semi-supine position after 5 minutes rest for the subject in a quiet setting without distractions using a completely automated device.

Vital signs (systolic and diastolic blood pressure, pulse rate, respiratory rate, and body temperature) will be measured after the subject has been in the supine position for at least 5 minutes at Visit 2 and Visit 7.

Summary statistics will be created per vital sign parameter and visit/timepoint (pre- and post-injection) for all scheduled treatment visits by treatment group including the absolute values per visit/timepoint and the absolute change from baseline.

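### Does testing IgG4 at the visit of the sixth injection, with no modelled contrast at Visit 10, leave this key secondary result unclear?

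*SAP*

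**What the plan says.** The endpoint in SAP Table 1 is "Serum grass-specific IgG4 at Visit 7 compared to baseline", and the Protocol's table of objectives and endpoints agrees. The objective attached to it is the effect of the 27,600 SU course on IgG4.

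The Protocol, under Dose/Dose schedule, states that "PQ Grass or placebo will be administered during Visits 2 to 7". Overall Design gives the active course as "6 injections of PQ Grass (900, 2700, 6000, 6000, 6000, 6000 SU sequentially"). The Schedule of activities marks both an injection and an immunoglobulin sample at Visit 7. The other immunoglobulin samples are at screening and Visit 10, and Overall Design describes the latter as "Visit 10 (during GPS").

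SAP 7.7.2.5 plans two things:

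- summaries by visit and arm of the absolute values and of the change from baseline, for both Visit 7 and Visit 10;
- a model for one of those changes only: "The change from baseline to Visit 7 in grass-specific IgG4 [mg/L] will be additionally analysed using the same linear mixed model", with baseline as an additional covariate.

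SAP 7.7.2 covers multiplicity: "The full 5.0% two-sided alpha for the Fallback method will be distributed across the 8 key secondary endpoints". For vital signs, SAP 7.8.4 does separate the time points: "Summary statistics will be created per vital sign parameter and visit/timepoint (pre- and post-injection) for all scheduled treatment visits by treatment group". SAP 7.8.1 counts treatment received at each visit, including "unscheduled injections for dose repeat and dose reduction". It also reports the cumulative SU received, its ratio to the planned dose, and a listing of every injection for any subject with a modified or additional dose.

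**The concern.** The objective names the full course, but the tested sample is taken on the day of the last injection. If blood is drawn first, the result describes five injections and not six, and neither SAP 7.7.2.5 nor the Schedule of activities gives the order. The SAP shows that it can make the distinction, because it does so for vital signs.

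Visit 10 is the only sample scheduled after all six injections, and the supplied text gives it no baseline-adjusted difference from placebo. A reader could conclude that a formally tested endpoint has an undefined exposure behind it, and that the one sample that fits the objective goes without an estimated treatment effect. At stake is how the IgG4 result is described. The primary endpoint and the error rate are not involved.

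**Working it through.** **1. Reproduce the stated course.** The doses come from the Protocol, Overall Design.

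900 + 2,700 + 4 × 6,000 = 27,600 SU. This matches the stated cumulative dose.

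**2. Scheduled dose before the Visit 7 sample.** Six injections over Visits 2 to 7 make Visit 7 the sixth.

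| Order at Visit 7 | Scheduled dose given | Share of course |
|---|---|---|
| Blood first | 900 + 2,700 + 3 × 6,000 = 21,600 SU | 21,600 / 27,600 = 78.3% |
| Injection first | 27,600 SU | 100% |

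The sixth injection is 6,000 / 27,600 = 21.7% of the course.

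**3. What that difference means for IgG4.** These are shares of dose, not of antibody response, and the documents give no response kinetics. In the second row the sixth dose precedes the sample only within the same visit. The fifth injection was given at Visit 6, about 4 weeks earlier (Protocol, Dose/Dose schedule). Assume that IgG4 does not change within a visit. The sample then mainly reflects the first five injections in both rows, and fixing the order would hardly change how the estimate reads.

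**4. Is the endpoint inconsistent?** The Protocol's endpoint table, SAP Table 1 and SAP 7.7.2.5 all say Visit 7 against baseline. The key secondary list is CSMS over the entire season, dSS peak, dSS entire, dMS peak, dMS entire, well days, RQLQ(S) and IgG4 at Visit 7. That is 1 + 2 + 2 + 1 + 1 + 1 = 8, which agrees with SAP 7.7.2. A Visit 10 model would be a ninth analysis and could carry no alpha.

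**5. What Visit 10 already gets.** SAP 7.7.2.5 plans values and changes from baseline by arm. SAP 7.1.1 specifies n, mean and SD for continuous data and, where appropriate, a two-sided 95% interval for each mean. From these a reader can form

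difference = mean(PQ Grass) − mean(placebo), SE = √(SD₁²/n₁ + SD₂²/n₂).

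Only the baseline-adjusted version is absent.

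**6. What a Visit 10 model would estimate.** The FAS in SAP Table 3 includes anyone with at least one injection, so a FAS model at Visit 10 is not strictly a contrast after a completed course. Visit 10 also falls in season. Natural exposure affects both randomised arms and does not invalidate the contrast, but the estimate describes a different setting from the one at Visit 7, since the injections are to be finished before the season starts.

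**7. Dose actually received.** Repeats and reductions mean that some subjects will depart from 21,600 or 27,600 SU. The rules for them are not in the public text, so no range can be calculated reliably. The counts by visit and the listing in SAP 7.8.1 let the dose before Visit 7 be largely recovered.

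**The case for a change.** The strongest argument for a change accepts step 3 and turns it round. If same-day order hardly matters because IgG4 does not respond that fast, then Visit 7 reflects mainly five injections in every case, and Visit 10 is the only sample that can speak to the full course named in the objective. The remedy would be cheap: one supportive model on samples already collected, with no alpha, and a sentence on draw order. The unadjusted difference that a reader can construct is also not the estimate that Visit 7 receives.

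Much of this stands as fact. In the supplied text the order is unstated, and there is no baseline-adjusted contrast at Visit 10. Two limits apply. First, the public protocol is abridged. SAP 6.3 refers back to the protocol for visits, and SAP 7.6 mentions an exploratory section that is not among the supplied text, so either item could sit there. Second, the argument shows that an extra estimate would be informative. It does not show that the planned one is wrong. Visit 7 is a fair choice: it is the last scheduled injection visit, its sample precedes the season, and the randomised comparison there is valid for what it claims, a difference between arms at that visit.

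The analogy with vital signs is weak. Those are summarised both before and after injection and need time labels, whereas the schedule shows a single immunoglobulin entry at Visit 7.

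**Conclusion.** No change to the plan is needed. The ambiguity is at most 6,000 of 27,600 SU (21.7% of the scheduled dose). On the assumption that IgG4 does not respond within one visit, it has little bearing on the result. That assumption comes from outside the documents. If it were wrong, the draw order would matter more, but the Visit 7 contrast would remain a valid randomised comparison. Type I error and the Fallback procedure are unaffected either way.

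Draw order is procedural detail that the full protocol would normally hold, and the report can state it. Exposure is already summarised and listed in SAP 7.8.1. Visit 10 is already reported by arm. The report should describe the IgG4 result as the response at the visit of the last scheduled injection, which is how the endpoint is already defined. A supportive Visit 10 model with a 95% interval would be a reasonable extra at the statistician's discretion. Leaving it out leads to no wrong estimate or conclusion.

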## 7.7.2.6. Standardised Rhinoconjunctivitis Quality of Life Questionnaire (RQLQ[S]) averaged over the peak GPS

## 7.7.2.6.1. Standardised rhinoconjunctivitis Quality of life questionnaire

Rhinoconjunctivitis quality of life will be assessed using the RQLQ(S). The RQLQ(S) is a questionnaire which consists of 28 questions in 7 domains (activity limitation, sleep problems, nose symptoms, eye symptoms, non-nose/eye symptoms, practical problems, and emotional function). Each question is scored on a scale from 0 to 6 (0 = not impaired at all to 6 = severely impaired). Subjects will be issued the RQLQ questionnaire at Visits 2, 9 and 10. The Visit 2 RQLQ will be the baseline RQLQ.

The total score defined as the mean of all 28 responses will be aggregated as an outcome variable on a subject level by taking the mean of the scores from Visits 9 and 10 that can be attributed to the peak GPS.

## 7.7.2.6.2. RQLQ[S] averaged over the peak GPS

The average total RQLQ score during the peak GPS will be calculated if at least one score at Visit 9 or 10 is reported during the peak GPS. It will be considered missing if the RQLQ questionnaire has not been filled at any of these visits or both visits do not fall within the peak GPS. Missing values of the RQLQ score will not be imputed.

The total RQLQ score and its change from baseline (Visit 2) will be summarised by visit and treatment group for the FAS. In addition, summary statistics will be created for the RQLQ during the peak GPS and its change from baseline.

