## **Table 3 Definition of analysis sets**

Analysis set	Description
Full Analysis Set (FAS)	All subjects who received at least 1 injection of the investigational drug/placebo. Subjects will be analysed according to the treatment they were randomised to.
Safety Set (SAF)	All subjects who received at least 1 injection of the investigational drug/placebo. Subjects will be analysed according to the treatment that they actually received.

The FAS will be the primary analysis set and will be used to evaluate efficacy. The SAF will be used for all evaluations of safety and tolerability. The criteria used for inclusion of each subject into the respective analysis sets are detailed in the BDRM plan and the final decisions are documented in the BDRM minutes.

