#### 6.7 Definition of Grass Pollen Season

For the purpose of statistical analysis, the start and end of the entire grass pollen seasons (GPS) and the peak pollen seasons of each year (if applicable) will be determined based on the daily pollen counts from pollen traps local to the trial sites. The final decisions regarding the site-specific (peak) pollen periods to be applied for the eDiary related endpoints will be determined prior to unblinding of the database and documented in the BDRM minutes for each year.

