## 7.7.1.4. Average CSMS over the peak GPS

The average CSMS over the peak GPS is calculated as the sum of the daily CSMS within the peak GPS divided by the number of days of the peak GPS where the CSMS has been collected or imputed.

For the primary analysis, all subjects in the FAS will be included. This will be done by using multiple imputation methods on a by-day level. The average CSMS over the peak GPS can then be calculated based on all days within the peak GPS per imputation.

An analysis providing summary statistics based on observed cases will also be performed

Summary statistics will be provided for the average CSMS over the peak GPS by treatment group based on observed cases.

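### Should missing peak-season RQLQ(S) scores be imputed, since the key secondary comparison otherwise uses fewer subjects than the FAS?

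*SAP*

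**What the plan says.** SAP 7.7.2.6.1 has the RQLQ(S) completed at Visits 2 (baseline), 9 and 10. The subject-level outcome is formed by "taking the mean of the scores from Visits 9 and 10 that can be attributed to the peak GPS". Under SAP 7.7.2.6.2 one in-peak score is enough. The outcome is missing if the questionnaire was filled at neither visit, or if "both visits do not fall within the peak GPS". It then states: "Missing values of the RQLQ score will not be imputed".

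The peak is fixed later. SAP 6.7 has the entire and peak seasons "determined based on the daily pollen counts from pollen traps local to the trial sites", with final decisions documented before unblinding. The protocol's Overall Design places Visit 9 at about the onset of the season and Visit 10 during it, and ties neither to the peak.

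On analysis sets, SAP 5.1 (Table 3) says: "The FAS will be the primary analysis set and will be used to evaluate efficacy". For the CSMS, SAP 7.7.1.4 says: "For the primary analysis, all subjects in the FAS will be included". SAP 6.2 limits imputation to the primary variable and the covariates of the CSMS model. SAP 7.7.2 tests the key secondary endpoints by the Fallback method, with the alpha "distributed across the 8 key secondary endpoints".

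**The concern.** Each subject has at most two in-season questionnaires, at visits not scheduled around the peak. A treated subject who withdraws before Visit 9, skips both questionnaires, or attends both visits outside the peak drops out of the comparison. The primary endpoint loses nobody in this way.

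The test is confirmatory. SAP Table 1 yields eight secondary efficacy endpoints only if RQLQ(S) is counted: well days, RQLQ(S), IgG4, CSMS over the entire season, and dSS and dMS each over the peak and the entire season. Under the Fallback method a significant test passes its alpha on, so power lost here could also weaken later tests. If withdrawal differed by arm, the observed-case difference could be biased as well. Data that could support an imputation are already collected: Visit 2 RQLQ(S), off-peak Visit 9 and 10 scores, and the daily CSMS.

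**Working it through.** **Is there a contradiction?** The FAS is the nominal efficacy set, but the promise that every FAS subject contributes is made for the primary analysis only (SAP 7.7.1.4), and SAP 6.2 does not extend imputation to RQLQ(S). The protocol's Statistical methods section says only that secondary endpoints will generally follow a similar approach to the primary. SAP 7.7.2.6.2 then sets a specific rule for RQLQ(S). The passages are compatible.

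**Inputs.** From the documents: N = 555 randomised in Year 1, allocated 1:1, and a two-sided Fallback alpha of 5% over 8 endpoints. The plan states no power, SD or evaluable count for RQLQ(S), so there is no figure to reproduce. The following are assumptions:
- f, the share of subjects with an in-peak score: 0.9, 0.7 and 0.5.
- r, the correlation of the peak score with all imputation predictors together: 0.65.
- ρ, its correlation with Visit 2 RQLQ(S) alone: 0.3 to 0.5.
- 90% power with complete data.
- Alpha of 5%, or 0.05/8 = 0.00625 if split equally.

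**Cost of using observed scores only.** The interval widens by 1/√f. Power is Φ[(z + 1.2816)√f − z], with z = 1.960 at alpha 0.05 and 2.734 at alpha 0.00625.

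| f | Evaluable of 555 | CI widening | Power, alpha 0.05 | Power, alpha 0.00625 |
|---|---|---|---|---|
| 0.9 | about 500 | 1.05 | 86.8% | 85.9% |
| 0.7 | about 389 | 1.20 | 77.4% | 73.4% |
| 0.5 | about 278 | 1.41 | 63.0% | 54.2% |

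**What imputation recovers.** Against an unadjusted observed-case analysis, the SE ratio is √(1 − r²(1 − f)). With r² = 0.4225:
- f = 0.9: √(1 − 0.04225) = 0.979, a cut of 2.1%.
- f = 0.5: √(1 − 0.21125) = 0.888, a cut of 11.2%. The SE stays 1.414 × 0.888 = 1.26 times that of complete data.

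That comparator flatters imputation. SAP 7.7.2.5 adjusts IgG4 for its baseline value. If RQLQ(S) is treated likewise, only the predictors beyond baseline help, and the ratio becomes √(1 − (1 − f)k), with k = (r² − ρ²)/(1 − ρ²).
- ρ = 0.3: k = 0.3325/0.91 = 0.365. The cut is 1.8% at f = 0.9 and 9.6% at f = 0.5.
- ρ = 0.5: k = 0.1725/0.75 = 0.230. The cut is 1.2% at f = 0.9 and 5.9% at f = 0.5.

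Dividing (z + 1.2816)√f by this ratio gives the power with imputation:
- f = 0.9: about 87 to 88% over both alphas, against 86 to 87% without.
- f = 0.5: about 61 to 72%, against 54 to 63% without.

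These figures assume that every subject without a peak score has the predictors. A subject who withdrew before the season has no in-season data. If all the missing 10% at f = 0.9 were such subjects, the gain over the unadjusted analysis would be nil.

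**Bias.** If withdrawers differ from the rest by δ points in both arms, the observed-case difference shifts by (w₁ − w₂)δ, where w₁ and w₂ are the withdrawal shares. Taking 10% against 5% and δ = 0.5 to 1 as assumptions, the shift is 0.05 × 0.5 = 0.025 to 0.05 × 1 = 0.05 points on the 0 to 6 scale. Imputation under missing-at-random would not remove it for those who left before the season, because nothing in their data shows that they were worse.

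**The case for a change.** The strongest case for a change is that f may be low. If the visits often miss the peak, up to half the subjects might carry no value, and power could fall from 90% to between 54 and 63%. Loss from visit timing is also where missing-at-random is most credible, and imputation would need no new data. That much stands: the released text gives neither an expected evaluable share nor a sensitivity analysis for missing RQLQ(S).

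Three things limit it. First, no passage supports a value near 0.5. The released protocol is a synopsis and the SAP is abridged, so visit windows relative to the peak, or the RQLQ(S) model itself, may be set out in text that is not available. Applying the site-specific peak to RQLQ(S) is itself a natural reading, since SAP 6.7 names only eDiary endpoints there.

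Second, the case for imputing is strongest exactly where the imputed result is least secure. With few observed scores, a confirmatory quality-of-life result would borrow heavily from the CSMS, which is the primary endpoint. Subjects with both visits off-peak never show how two off-peak scores together predict a peak score.

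Third, part of the transparency sought is already planned. SAP 7.7.2.6.2 summarises peak RQLQ(S), and the standard statistics in SAP 7.1.1 include the number of subjects with data, by treatment group. SAP 7.2 tabulates reasons for discontinuation and attendance per visit by arm. Only a breakdown of why a peak score is missing would be new.

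**Conclusion.** No change follows. The comparison will probably use fewer subjects than the FAS, by an amount the documents do not give, but the rule is explicit, pre-specified and valid if followed. Loss from visit timing is plausibly unrelated to treatment under blinding and mainly costs precision. With 90% of subjects evaluable the cost is a 5% wider interval, and imputation would cut the standard error of a baseline-adjusted analysis by only about 1 to 2%. With 50% evaluable the cut would be 6 to 10%, bought by resting a confirmatory test on modelled scores. The illustrated withdrawal bias, 0.025 to 0.05 points, is small and would remain for subjects who left before the season.

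These figures rest on assumed values of f, r, ρ and withdrawal, and on a baseline-adjusted model that the released RQLQ(S) text does not show. Whether to impute here is a fair trade-off on which statisticians may differ. Imputation as a sensitivity analysis, or a table of reasons for missing scores, would be a reasonable extra, but the planned test does not depend on either.
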